 - a. Women of non-childbearing potential (WONCBP), or
 - b. Women of childbearing potential (WOCBP) with a negative pregnancy test at screening and must agree to use protocol defined methods of contraception for the duration of the study.
 7. Males with female partners of childbearing potential must agree to use protocol defined methods of contraception and agree to refrain from donating sperm for the duration of the study.
 8. Willing and able to give informed consent.

Note: If both eyes meet the inclusion criteria, the eye with the best visual acuity at the screening visit will be designated as

the study eye. If both eyes have the same visual acuity, the right eye will be used as the study eye.

Exclusion Criteria: Unless specified otherwise, ocular specific exclusion criteria apply to the study eye only.

1. GA due to causes other than AMD such as Stargardt disease, cone rod dystrophy or toxic maculopathies like plaquenil maculopathy.
2. Spherical equivalent of the refractive error demonstrating > 6 dioptres of myopia or an axial length of >26 mm.
3. Evidence of exudative (wet) AMD including evidence of retinal pigment epithelium rips or evidence of neovascularization anywhere in the retina based on fluorescein angiogram as assessed by the PI in either eye within 12 months.
4. Retinal disease likely to confound visual performance or be affected by intraocular steroid.
5. Any ophthalmologic condition that reduces clarity of the media and that, in the opinion of the investigator interferes with ophthalmologic examination (e.g. advanced cataract or corneal abnormalities).
6. Any ophthalmologic condition that prevents adequate imaging of the retina judged by the PI.
7. Intraocular surgery (including lens replacement surgery) within 3 months prior to dosing.
8. Aphakia or absence of the posterior capsule. Previous violation of the posterior capsule is also excluded unless it occurred as a result of yttrium aluminum garnet (YAG) laser posterior capsulotomy in association with prior

posterior chamber intraocular lens implantation and at least 60 days prior to Day 0.

9. Any ophthalmologic condition that may require surgery during the study period.
10. Glaucoma or family history of glaucoma.
11. Any contraindication of IVT injection including current ocular or periocular infection.
12. History of uveitis or endophthalmitis.
13. History of choroidal neovascularization (CNV) in either eye.
14. History of IVT injection of steroids within 12 months.

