The presence of drusen and pigmentary abnormalities in the central macula is the main ocular risk factor for late age-related macular degeneration. The greater the area of drusen at the macula the greater the risk of progression to loss of vision. Using the direct ophthalmoscope or a slit lamp these early changes can be detected.

AMD is a highly complex disease that is affected by multiple factors, such as ageing, genetic predisposition, environmental elements, oxidative stress and inflammatory effects [2, 5, 6]. Smoking, age, alcohol consumption, diet and obesity are important risk factors related to oxidative stress [6, 7]. High body mass index, cardiovascular disease, hypertension and a variety of dietary patterns are risk factors less consistently[8]. Several single-nucleotide polymorphisms (SNPs) that confer increased or decreased risk of inflammation have been identified. They include the well-recognized *complement factor H* (CFH), *CX3CR1*, *Toll-like receptor 3* (TLR3), TLR4, and *interleukin 8* (IL-8)[9]. Although AMD is not a classic inflammatory disease, inflammatory cells have an important role in AMD pathogenesis and progression [5, 10, 11]. Evidence has also suggested that some infectious agents are associated with AMD.

Although relatively simple to diagnose through direct visualization augmented with rapid sequence fluorescein angiography, treatment has presented a far greater challenge because the true etiology of AMD is largely unknown [12]. Within the past decade, researchers have introduced many new, potentially promising treatment and prevention

options in an attempt to minimize the damage imparted from AMD. The current standard-of-care for the treatment of exudative AMD are the anti-VEGF agents, such as ranibizumab (Lucentis®), aflibercept (Eylea®) and off-label bevacizumab (Avastin®) [13]. No therapy exists for GA which is usually bilateral and relentlessly progressive. Dexamethasone and triamcinolone acetonide (TA) are the commonly used corticosteroids for macular oedema [14, 15]. Most studies showed their effectiveness in improving vision function and reducing macular oedema. Nevertheless, intravitreal injection of corticosteroids carries significant complication risk such as cataract progression, ocular hypertension and endophthalmitis.

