6.2 SUBJECT ENROLLMENT

It is the responsibility of the investigator to ensure that subjects are eligible to participate in the study prior to enrollment and throughout the study. Documentation of the personally signed and dated informed consent of each subject, using the study-specific ICF, is required before initiating the Screening process. After written informed consent has been obtained and eligibility to participate established, investigative site personnel will obtain the subject's identification number. Only eligible subjects will be allocated to the open label FCA 1 mg/0.1mL or 2mg/0.1 mL.

Enrollment will occur in two parts in order to minimise the likelihood that subjects will be exposed to risks. During part 1 & 2, subjects will be screened one by one as only one patient will initially be enrolled during part 1 of the trial. The first enrolled subject will participate in a screening period of up to 14 days and a follow-up period of 28 days, to detect an IOP response.

After first subject has completed the follow-up of 28 days after FCA 1mg/0.1 mL injection, The subject's safety data will be reviewed the safety data of this will be reviewed by an independent safety review committee to determine whether to commence enrolment of additional 2 patients in the first cohort of 1mg/0.1mL dose of FCA. Enrolment will be stopped if >2 patients experience limiting-toxicity adverse event related to the study drug. If no more than two adverse events considered to be related to the study drug occur with limiting toxicity, the second cohort will be recruited. Dose-limiting toxicity is defined by intraocular inflammation, elevated IOP, reduced vision (loss of ≥ 15 letters), or haemorrhage within 28 days after injection.

Part 2 will take in place if the 3 subjects have tolerated well the dose. Part 2 initially involves a single subject treated with 2mg/0.1mL FCA to assess safety and tolerability. This subject will be followed for up to 28 days and reviewed by an independent safety

review committee prior to the recruitment of a further 5 subjects treated with 2mg/0.1mL FCA totalling in 6 subjects in the second cohort.

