7.8 POST-INJECTION ASSESSMENT

The study eye will be assessed before and after injection to ensure that the injection procedure and/or the study medication have not endangered the health of the eye. The initial post-injection assessment should be done within 15 minutes' post-injection and

include a gross assessment of vision (light perception) and monitoring IOP. If subject passes gross vision test and IOP is < 30mmHg, the subject may leave the site. If subject fails gross vision test and/or IOP is > 30 mmHg, assessments will continue every approximately 30 minutes until the subject passes gross vision test and IOP is < 30 mmHg.

Any subject who develops a significant and sustained raise in IOP (> 30 mmHg) or a non-adequately perfused central retinal artery (CRA) after injection, should be monitored according to the PI’s clinical judgment and may undergo additional procedures and measurements of IOP beyond those specified in the protocol as well as IOP lowering procedures. If any concern or immediate toxicity is noted, the subject will remain at the site and will be treated according to the PI’s clinical judgment.

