7.10.3 ADVERSE EVENTS OF SPECIAL INTEREST

An adverse event of special interest is one of scientific and medical concern specific to the Sponsor's product or program where ongoing monitoring and rapid communication by the Investigator to the Sponsor may be appropriate. These adverse events may be serious or non-serious. Applicable adverse events may require further investigation in order to characterize and understand, and depending upon the nature of the event, rapid communication by the trial Sponsor to other parties may also be required. These adverse events of special interest must be reported using the same mechanism and timeframe (i.e. within one working day of the Investigator's or delegate's knowledge of the event) as described for serious adverse events in Section 7.9.2. The adverse events of special interest include the following:

- Endophthalmitis
- 4+ ocular inflammation

- 2-3+ ocular inflammation that fails to decrease to 1+ or less within 30 days of the onset of the event
- Sustained (> 5 minutes) loss of light perception after FCA injection
- Sustained elevation of IOP (30 mmHg) at/past 90 minutes' post-injection
- Any elevation of IOP requiring surgical intervention (i.e. paracentesis)
- New vitreous hemorrhage of > 2+ severity that does not resolve within 14 days of the onset of the event
- Cataract progression

If an adverse event of special interest occurs in a study subject, the study subject will be followed for resolution of the adverse event. A decision will be made by the Sponsor concerning further exposure to the study treatment and further participation in the study.

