9.7 DATA SAFETY MONITORING BOARD

An independent DSMB will be convened. The mission of the DSMB will be to ensure the ethical conduct of the trial and to protect the safety interests of patients in this study. The DSMB will be responsible for reviewing the cumulative safety results from the study. The DSMB will meet prior to the commencement of the study, and will review all

available safety/tolerability data (e.g., adverse events, serious adverse events, clinical laboratory assessments, blood pressure, haematology, urology) at Day 0 and 1 month after IVT injection of FCA of the initial participant in Part 1 and 3 (prior to Part 2 & 4 of the study), and convene as required throughout the study period to review data and potential safety risks. The criteria for evaluating study continuation will relate to study safety, including the incidence and severity of ocular and/or systemic side effects not limited to but including; change in IOP of >10mmHg, a loss of 15 letters or more in BCVA, presence or intraocular inflammation, presence or absence of ocular pain, change in BP of 30mmHg (systolic or diastolic), incidence of hospitalisation or systemic illness, and any other ocular or systemic adverse events reported. Any changes will be referenced to baseline measurements. The DSMB will then meet at the conclusion of the study and after the final statistical analysis in order to review all data.

DSMB will consist an ophthalmologist, and a biostatistician, both independent of the study team.

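### Read under the study-eye-only header, exclusion 10 bars a relative's glaucoma but not the patient's own fellow-eye glaucoma; no criterion uses entry IOP, and the IOP safety rules disagree on whether baseline counts

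*Protocol*

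**What the plan says.** **Eligibility (Protocol, Section 1.1).** The exclusion list opens with "Unless specified otherwise, ocular specific exclusion criteria apply to the study eye only". Exclusion 10 is "Glaucoma or family history of glaucoma". Exclusion 13 is "History of choroidal neovascularization (CNV) in either eye", and exclusion 3 (exudative AMD) also names either eye. Exclusion 12 (uveitis, endophthalmitis) names no eye.

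**IOP measurement.** Section 7.6 has IOP measured in both eyes at Visit 1 and in the study eye afterwards. Section 6.3.2 has it measured again on Day 0 before the injection.

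**IOP as a safety outcome.**
- Section 6.2, as in the Synopsis: "Dose-limiting toxicity is defined by intraocular inflammation, elevated IOP", continuing with vision loss and haemorrhage, within 28 days.
- Section 7.8: "If subject passes gross vision test and IOP is < 30mmHg, the subject may leave the site".
- Section 7.10.3, as an adverse event of special interest: "Sustained elevation of IOP (30 mmHg) at/past 90 minutes' post-injection".
- Section 9.7, among the DSMB's continuation criteria: "change in IOP of >10mmHg", with changes referred to baseline.

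**Background.** Section 2.2 says that "intravitreal injection of corticosteroids carries significant complication risk such as cataract progression, ocular hypertension and endophthalmitis".

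**The concern.** There are two separate gaps.

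The first is scope. Family history belongs to the person, not to an eye, so exclusion 10 appears meant to keep out people with a personal or familial link to glaucoma. The header cuts the personal half of that criterion back to the study eye. The result is stricter about a relative's disease than about the patient's own.

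The second is that IOP enters the safety rules in several forms and enters eligibility in none. Section 6.2 gives detection of an IOP response as the purpose of the first subject's 28-day follow-up, and elevated IOP is a DLT. If the DLT is not tied to baseline and entry pressure is not considered, a pressure that was already high before dosing may be hard to tell from a drug effect. With three patients in the 1 mg cohort, one disputed event matters for the escalation decision.

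**Working it through.** The plan gives no calculated figure on this point. The check is a comparison of the text, with a little arithmetic to show scale.

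**Step 1: scope of exclusion 10.** The header limits ocular criteria to the study eye unless a criterion says otherwise. Exclusions 3 and 13 say otherwise; exclusions 10 and 12 do not. Applied literally:
- glaucoma in the study eye: excluded;
- glaucoma in a relative: excluded;
- glaucoma in the fellow eye only: not excluded.

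**Step 2: use of IOP at entry.** None of the 8 inclusion and 19 exclusion criteria gives an IOP value or names ocular hypertension. Exclusion 4 concerns retinal disease. Exclusion 11 (contraindication to intravitreal injection) is general and states no pressure.

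**Step 3: the IOP safety rules side by side.**

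| Rule | Value | Baseline reference | Attribution to drug |
|---|---|---|---|
| DLT, Synopsis | none given | none | not stated |
| DLT, Section 6.2 | none given | none | required in the stopping rule |
| Leaving the site, Section 7.8 | 30 mmHg | none | not applicable |
| Special interest, Section 7.10.3 | 30 mmHg | none | not stated |
| DSMB, Section 9.7 | change > 10 mmHg | yes | not stated |

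**Step 4: how far the absolute and relative rules diverge.** For entry IOP b (assumed; the protocol gives no distribution), the rise that reaches 30 mmHg is 30 − b. The DSMB criterion, taken as a rise, is met above b + 10.

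| Entry IOP b (mmHg) | Rise to reach 30 | DSMB criterion met above |
|---|---|---|
| 15 | 15 | 25 |
| 20 | 10 | 30 |
| 25 | 5 | 35 |
| 27 | 3 | 37 |
| 29 | 1 | 39 |

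The two agree only near 30 − 10 = 20 mmHg. An eye entering at 30 mmHg or more meets the leave-site condition only if its pressure falls.

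**Step 5: what one such event could do.** Section 5.2.1 escalates if no DLT is seen in three patients and does not mention attribution. Section 6.2 stops enrolment only if more than two patients have a drug-related limiting toxicity, and recruits the second cohort otherwise. Its next paragraph makes Part 2 depend on the three subjects having tolerated the dose.

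Let q be the chance that a patient has an elevated-IOP call caused by entry pressure alone. The documents give no value, so q is assumed, with patients independent.
- At least 1 of 3 (Section 5.2.1): 1 − (1 − q)³ = 14.3% at q = 0.05, 27.1% at 0.10, 48.8% at 0.20.
- At least 3 of 9 (the more-than-two rule, if all such calls counted): upper binomial tail = 0.8%, 5.3%, 26.2%.

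These figures show only how much depends on which rule governs. They do not estimate how often it would happen.

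**The case against.** **Exclusion 10 may already be meant at person level.** A family history cannot apply to one eye, so a sensible investigator may read the whole criterion as covering the patient. That is a fair reading of intent and makes this an ambiguity more than a proven gap. It does not rescue the wording: the header requires an exception to be stated, and exclusions 3 and 13 show how the protocol states one.

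**A reader might infer that an eye entering near 30 mmHg would be counted as a drug toxicity.** The documents do not support that. The 30 mmHg figure governs leaving the site and special-interest reporting, and neither is a DLT. Section 6.2 counts events related to the drug, Section 7.10.4.2 has an unrelated category that covers disease, and the DSMB works from baseline. These safeguards reduce the risk of miscounting but do not remove it. The Synopsis and Section 5.2.1 state no attribution, and the possibly-related category admits events that disease could also explain.

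**The effect on escalation depends on a separate conflict.** Under the more-than-two rule in Section 6.2, one event does not prevent the second cohort; under Section 5.2.1 it does. This objection stands. An entry limit alone would leave the DLT undefined and the escalation rules in conflict.

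**Investigator judgement is available.** Exclusion 11, and exclusion 9 on conditions that may need surgery, could be used to keep out an eye with high pressure. Neither says when.

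**A reader might also infer that patients with fellow-eye glaucoma are the ones most at risk of a steroid pressure rise.** Section 2.2 names ocular hypertension as a risk of intravitreal corticosteroids but does not rank patients, so that claim has no support here.

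**Conclusion.** The point holds in two parts.

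1. As written, exclusion 10 excludes a relative's glaucoma and not the patient's own fellow-eye glaucoma. This is at odds with the person-level intent of the family-history clause and with how exclusions 3 and 13 are worded. It rests on a literal reading of the header.

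2. Entry IOP is measured but plays no stated part in eligibility, while the IOP safety rules mix an unquantified term, an absolute limit and a change from baseline. An eye with high entry IOP could be counted as a DLT and, if Section 5.2.1 governs, could block escalation. Whether it would is not fixed by the text, and how often cannot be estimated because the protocol gives no IOP distribution.

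The two parts are independent: fellow-eye glaucoma says nothing about the study eye's entry pressure. The 20 mmHg at which the two rules meet is arithmetic, and should not be read as an entry ceiling.

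**What to change.** - Reword exclusion 10 so that glaucoma in either eye excludes, and confirm whether exclusion 12 is meant for the study eye or either eye.
- Have the sponsor state whether and how screening and Day 0 IOP bear on eligibility. Any value, and any further pressure-related exclusion, is for the sponsor to set.
- Reconcile the IOP wording in the Synopsis and Sections 5.2.1, 6.2, 7.8, 7.10.3 and 9.7. State whether an IOP DLT is judged as a change from baseline, whether it must be drug-related, and which escalation rule governs.

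The cost is a protocol amendment. IOP is already measured in both eyes at screening and in the study eye on Day 0, so no new procedure is needed. There may be some additional screen failures; the number is unknown.

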1.2 SCHEDULE OF ACTIVITIES (SOA)

	Screening Day -14 to -1	Baseline Visit 1, Day 0	Study Visit 2 Day 1 +/-1 day	Study Visit 3 Day 7 +/- 1 day	Study Visit 4 Day 14 +/-1 day	Study Visit 5 Day 28 +/-1 day	Study Visit 6 Day 60 +/-1 day	Study Visit 7 Day 90 +/-1 day	Final Study Visit 8 Day 150 +/-1 day
Procedures									
Informed consent	X								
Demographics	X								
Medical history	X								
Concomitant Medications	X	X	X	X	X	X	X	X	X
Adverse event review			X	X	X	X	X	X	X
Administer study intervention		X							
Physical exam	X	X			X			X	X
Vital signs	X	X	X	X	X	X	X	X	X
Best corrected visual acuity (BCVA)	X	X	X	X	X	X	X	X	X
Height and Weight	X						X		X
Visual Function Questionnaire (VFQ-25)		X							X
Goldmann Intraocular Pressure (IOP)	X	X	X	X	X	X	X	X	X
Slit lamp biomicroscopy, incl. lens grading	X	X	X	X	X	X	X	X	X
Dilated ophthalmoscopy	X	X	X	X	X	X	X	X	X
SD-OCT	X	X	X	X	X	X	X	X	X
FAF and NIFR	X	X	X	X	X	X	X	X	X
Colour Fundus Photography	X						X		X
Fluorescein angiogram	X								X
Haematology & Urinalysis	X	X		X		X			X
Serum chemistry ^a	X	X		X		X			X
Urine Pregnancy test ^b	X								X
Pharmacokinetic sampling		X		X		X			X
Complete Case Report Forms (CRFs)	X	X	X	X	X	X	X	X	X
a: Albumin, alkaline phosphatase, total bilirubin, bicarbonate, BUN, calcium, chloride, creatinine, glucose, LDH, phosphorus, potassium, total protein, AST, ALT, sodium. b: Serum pregnancy test (women of childbearing potential).									

1.3 ABBREVIATIONS

AE	Adverse event
AMD	Age-related macular degeneration
BCVA	Best corrected visual acuity
DCFP	Digital colour fundus photography
CNV	Choroidal neovascularization
CRC	Central reading centre
CRF (eCRF)	Case report form (electronic CRF)
CRO	Contract research organization
DSMB	Data safety monitoring board
CTCAE	Common Terminology Criteria for Adverse Events
ETDRS	Early treatment diabetic retinopathy score
FA	Fluorescein angiogram
FAF	Fundus autofluorescence
FCA	Fludrocortisone acetate
FSH	Follicle-Stimulating Hormone
GA	Geographic atrophy
GCP	Good Clinical practice
HIPAA	Health Insurance Portability and Accountability Act
ICF	Informed consent
IEC	Independent Ethics Committee
IOP	Intraocular pressure

IRB	Institutional Review Board
ITT	Intention-to-treat
IVT	Intravitreal
LFT	Liver Function test
LH	Luteinising Hormone
LL-BCVA	Low luminance best corrected visual acuity
LOCS II	Lens Opacities Classification Systems III
MedDRA	Medical dictionary for Regulatory Activities
Mg	Milligram
mITT	Modified intention to treat
ML	Millilitre
mmHg	Millimetre of mercury
NIFR	Near-Infrared Fundus Reflectance
OCT	Optical coherence tomography
PI	Principal investigator
PK	Pharmacokinetics
QC	Quality control
RBC	Red blood cell
RPE	Retinal pigment epithelium
SAE	Serious adverse event
SD-OCT	Spectral-domain optical coherence tomography
SMC	Safety monitoring committee
SoA	Schedule of Activities

TEAE	Treatment emergent events
VA	Visual acuity
VEGF	Vascular endothelial growth factor
VFQ	Visual Function Questionnaire
WBC	White blood cell
WOCBP	Women of child bearing potential
WONCBP	Women of non-child bearing potential
YAG	Yttrium aluminium garnet

CONFIDENTIAL

2 INTRODUCTION

2.1 BACKGROUND

This study is being conducted for the clinical development of intravitreal Fludrocortisone acetate (FCA) for advanced Age-related Macular Degeneration (AMD) (geographic atrophy [GA]). The trial will be conducted in compliance with this protocol, Good Clinical Practice (GCP), and applicable regulatory requirements. The subject population will be comprised of adult male and female subjects with GA secondary to AMD.

2.2 AGE-RELATED MACULAR DEGENERATION

Age-related macular degeneration is the leading cause of severe vision loss in people over the age of 65 in the United States and other Western countries[1]. In the United States, about 1.75 million people have the advanced forms of AMD [2, 3]. The early signs of AMD (drusen and pigmentary changes) are common in individuals over age 65 and precede the advanced forms, which are visually devastating. The advanced forms of AMD are classified into either macular neovascularization (neovascular, wet, or exudative AMD) or GA.

Exudative AMD is characterized by the abnormal growth of choroidal vessels into the subretinal space. The subsequent exudation of fluid, lipid and blood causes retinal edema resulting in vision loss and symptoms of metamorphopsia. The growth of these new vessels is accompanied by the proliferation of fibrous tissue; the continued growth of these fibroblastic lesions into the macula results in progressive, severe and irreversible vision loss. Although exudative AMD is only present in about 10% of all AMD cases, the majority (90%) of the severe rapid visual loss due to advanced AMD is attributable to the development of macular neovascularization[4]. Without treatment, most affected eyes will develop poor central vision (20/200) within 12 months. Anti-VEGF agents, such as ranibizumab (Lucentis®), aflibercept (Eylea®) and off-label

bevacizumab (Avastin®), are the current standard-of-care for the treatment of exudative AMD.

Geographic Atrophy is a disease characterized by thinning and loss of the retinal pigment epithelium (RPE) and concurrent atrophy of photoreceptors and choriocapillaris[4]. Clinically, GA is characterized by islands of dead retinal cells in the back of the eye that gradually expand. Although GA can result in significant visual function deficits in reading, night vision, and dark adaptation, and produce dense, irreversible scotomas in the visual field, the initial decline in VA may be relatively limited if the fovea is spared. When the fovea is involved, GA quickly causes blindness. GA is responsible for approximately 20% of all legal cases of blindness in North America with increasing incidence and prevalence owing to a higher life expectancy.

The presence of drusen and pigmentary abnormalities in the central macula is the main ocular risk factor for late age-related macular degeneration. The greater the area of drusen at the macula the greater the risk of progression to loss of vision. Using the direct ophthalmoscope or a slit lamp these early changes can be detected.

AMD is a highly complex disease that is affected by multiple factors, such as ageing, genetic predisposition, environmental elements, oxidative stress and inflammatory effects [2, 5, 6]. Smoking, age, alcohol consumption, diet and obesity are important risk factors related to oxidative stress [6, 7]. High body mass index, cardiovascular disease, hypertension and a variety of dietary patterns are risk factors less consistently[8]. Several single-nucleotide polymorphisms (SNPs) that confer increased or decreased risk of inflammation have been identified. They include the well-recognized *complement factor H* (CFH), *CX3CR1*, *Toll-like receptor 3* (TLR3), TLR4, and *interleukin 8* (IL-8)[9]. Although AMD is not a classic inflammatory disease, inflammatory cells have an important role in AMD pathogenesis and progression [5, 10, 11]. Evidence has also suggested that some infectious agents are associated with AMD.

Although relatively simple to diagnose through direct visualization augmented with rapid sequence fluorescein angiography, treatment has presented a far greater challenge because the true etiology of AMD is largely unknown [12]. Within the past decade, researchers have introduced many new, potentially promising treatment and prevention

options in an attempt to minimize the damage imparted from AMD. The current standard-of-care for the treatment of exudative AMD are the anti-VEGF agents, such as ranibizumab (Lucentis®), aflibercept (Eylea®) and off-label bevacizumab (Avastin®) [13]. No therapy exists for GA which is usually bilateral and relentlessly progressive. Dexamethasone and triamcinolone acetonide (TA) are the commonly used corticosteroids for macular oedema [14, 15]. Most studies showed their effectiveness in improving vision function and reducing macular oedema. Nevertheless, intravitreal injection of corticosteroids carries significant complication risk such as cataract progression, ocular hypertension and endophthalmitis.

Because of the substantial amount of evidence suggesting the underlying role of inflammation in AMD, it is logical to target the specific molecules involved in inflammatory pathways [16, 17]. Corticosteroids were among the first anti-inflammatory drugs evaluated for treating choroidal neovascularization in AMD patients [16]. Although the anti-inflammatory mechanism of corticosteroids is not fully understood, in addition to the anti-inflammatory effects, corticosteroids can directly and indirectly reduce the permeability of choroidal endothelial cells and the outer blood retina barrier, inhibit the activation of matrix metalloproteinase, and suppress vascular endothelial growth factor (VEGF) expression [18]. Because VEGF and inflammatory cells closely interact with each other, inhibition of VEGF might strengthen the anti-inflammatory activity in AMD. The downregulation of inflammatory agents and inhibition of blood vessel permeability are regarded as the main goals of AMD treatment [16].

